Unique Protocol ID: 2024-01/33

Official Title: Effect of Postoperative Oral Rinsing on Thirst-Related Discomfort, Comfort Level, and Bowel Movement in Individuals Undergoing Abdominal Surgery: A Randomized Controlled Trial

NCT ID not yet assigned

Date of Document: January 18, 2024

Study Design

This study was conducted as a randomized controlled trial with pre-test and post-test design, involving intervention and control groups.

Study Setting and Duration

The research was carried out at the Department of General Surgery, Sivas Cumhuriyet University Research and Training Hospital, between June 5 2024, and December 5, 2024.

Study Population and Sample

The study population included patients who underwent abdominal surgery in the general surgery clinic during the study period. The sample size was calculated using G*Power 3.1.9.7 software by a biostatistics expert. With an effect size of 0.50, $\alpha=0.05$, and power=0.85 ($\beta=0.15$), the required sample size was determined to be 82 patients (41 in the intervention group and 41 in the control group). The actual study was completed with 98 patients (49 per group), considering potential data loss. Eligible patients were stratified based on diagnosis and randomized using block randomization with a random number table in a 1:1 allocation ratio.

Inclusion and Exclusion Criteria

The study included patients who were able to communicate, aged 18 or older, agreed to participate, and were scheduled for elective surgery.

Patients were excluded if they were over 80 years old, had a mental disorder that prevented them from rinsing their mouth, were unconscious after surgery, were at risk of swallowing water during rinsing, and underwent emergency surgery.

Patients who refused to complete the post-test and those requiring intensive care after surgery were excluded.

Data Collection Tools

Four tools were used:

1. Mini Mental State Assessment Test: The Mini Mental State Assessment (MMSA) is a common screening tool to systematically and comprehensively assess individuals' cognitive status. The test consists of 11 items assessing five cognitive domains: orientation, registration, attention and calculation, recall, and language. The maximum score that can be obtained from the scale is 30, and scores of 23 or below suggest cognitive impairment. The administration time, approximately 5–10 minutes, makes the tool suitable for routine use in clinical and research settings. Its validity and reliability in Turkish were conducted.

2. Personal Information Form: The questionnaire, which included the participants' descriptive and clinical characteristics, was developed by the researchers in two sections based on literature and clinical observations. The first section consisted of seven questions covering the patient's descriptive characteristics, including age, gender, and education level, in line with the study group, and the patient's clinical characteristics, including diagnosis, preoperative fasting time, postoperative oral intake time, and the time to start oral intake. The second section included a chart created for recording bowel sounds.

3. Surgical Period Thirst Discomfort Scale (SPTDS): The original seven-item scale was removed due to the low factor analysis of one item in the Turkish validity and reliability study. It was adapted as six items using a three-item Likert-type scale. Ratings are as follows: "Didn't Bother (0)," "A Little Bit Bothered (1), and "A Lot Bothered (2). The scale items are: "My Mouth is Dry," "My Lips are Dry," "My Saliva is Thick," "My Throat is Dry," "I Have a Bad Taste in My Mouth," and "I Want to Drink Water." The minimum score for the total scale is 0, and the maximum score is 12. As the score obtained from the scale increases, the level of discomfort related to thirst also increases.

4. Comfort Level Determination Scale - VAS: The comfort level of the individuals participating in the study will be determined using the Visual Analog Scale-10 (VAS-10). The scale is a 10-cm straight line with points spaced 1 cm apart. Each point on this straight line will be evaluated as a score for the comfort level, with the starting point being "0 = Lowest Comfort Level" and "10 = Highest Comfort Level." As the score obtained from the scale increases, the comfort level also increases.

Intervention Procedure

Before initiating the main study, a pilot application was conducted with a total of eight patients—four from the experimental group and four from the control group—to evaluate the data collection instruments and the implementation process. The results of the pilot study indicated that all scale items were found to be clear and understandable by the participants, and the average response time ranged between 10 and 12 minutes. No technical or logistical problems were encountered during the process, and the main study was subsequently initiated. Data obtained from the pilot study were not included in the main sample.

During the pilot phase, data collection instruments were administered to the experimental group patients after each oral rinse. However, as patients provided near-perfect responses across all measurements, a potential risk of bias was identified. Therefore, in the main study, the data collection instruments were administered only before the first oral rinse and after the completion of all three rinses.

The purpose of the study was explained to all participants, and written informed consent was obtained. Data were collected face-to-face by the researchers.

In the experimental group, postoperative cognitive assessment was conducted, and patients scoring 23 or higher on the MMSE (Mini-Mental State Examination) were instructed to perform oral rinsing three times at 20-minute intervals, each time using 20 ml of distilled water. Two graduated plastic cups were used for each rinsing: one containing 20 ml of distilled water and one empty cup for spitting out the rinse water. This setup enabled the evaluation of whether patients swallowed the water; none of the patients did, and all participated in the procedure compliantly. Data collection forms were administered face-to-face before the first rinse and 15 minutes after the final rinse, and bowel sounds were auscultated.

In the control group, postoperative cognitive assessment was also conducted, and patients scoring 23 or higher on the MMSE were administered the data collection forms and had their bowel sounds auscultated. No intervention was applied to this group. The data collection forms were re-administered 75 minutes later, in a manner consistent with the experimental group, and bowel sounds were re-evaluated.

To ensure consistency and avoid inter- or intra-group differences, all bowel sound assessments were performed using the same brand and model of stethoscope, and each patient's bowel sounds were auscultated for one minute. Considering the oral rinsing process, the total time required for data collection in the experimental group was approximately 20–25 minutes.

Data Analysis

SPSS 22.00 package program was used to analyze the data. Skewness-Kurtosis analyses were performed to determine the conformity of the data to a normal distribution. A Skewness-Kurtosis value between +1.96 and -1.96 is considered a normal distribution. All data used in the study were within the normal range, and the data showed a normal distribution. Frequency (n) and percentage (%) distributions were calculated to determine the sociodemographic and clinical characteristics of the participants. A t-test for independent samples was used to determine the mean differences between two independent groups, a t-test for dependent samples was used to compare pre- and post-intervention measurements, and a single-factor analysis of variance (ANOVA) was used for repeated measures. Cohen's d effect size was calculated to assess the significance of the difference between the groups in terms of the intervention. Statistical significance was accepted as $p<0.05$.

RESULTS

The mean age of the participants in the experimental group was 56.41 ± 14.80 years, while in the control group it was 55.78 ± 14.00 years. Overall, 57.1% of the participants were female. Among the patients, 46.9% of those in the experimental group and 42.9% in the control group were primary school graduates.

Clinically, 49% of the patients underwent surgery for cholecystectomy. The preoperative fasting period ranged between 7–18 hours in the experimental group, with a mean of 11.78 ± 2.47 hours, and between 8–36 hours in the control group, with a mean of 12.78 ± 4.33 hours.

The postoperative oral intake initiation time in the experimental group ranged between 6–20 hours, with a mean of 10.41 ± 4.64 hours, while in the control group it ranged between 2–66 hours, with a mean of 15.20 ± 11.57 hours. The

difference between the two groups was statistically significant ($t=-2.635$, $p=0.010$), indicating that patients in the experimental group began oral intake earlier than those in the control group. All patients in the experimental group started oral intake within 6–24 hours, whereas 88% of the control group started within 6–24 hours, 8% between 24–48 hours, and 4% after more than 48 hours. This difference was also statistically significant ($\chi^2=6.391$, $p=0.041$), again showing that oral intake began earlier in the experimental group.

Before mouth rinsing, the mean VAS Comfort Level score in the experimental group was 3.59 ± 1.29 , the mean Surgical Thirst Discomfort Scale (SPTDS) score was 8.00 ± 2.84 , and the mean number of bowel sounds was 3.49 ± 1.06 . In the control group, the initial mean VAS Comfort Level score was 4.02 ± 1.71 , the mean SPTDS score was 8.14 ± 2.74 , and the mean number of bowel sounds was 4.06 ± 1.52 . No significant differences were found between the groups in terms of VAS Comfort Level ($t=1.399$, $p=0.165$) or SPTDS ($t=-0.253$, $p=0.801$), indicating similar baseline comfort and thirst discomfort levels. However, the difference in bowel sound frequency was significant ($p<0.05$), favoring the control group, with a moderate effect size (Cohen's $d=0.44$).

After oral rinsing, the mean VAS Comfort Level score in the experimental group increased to 7.33 ± 1.14 , while in the control group's second measurement it was 3.86 ± 0.94 . This difference was statistically significant ($t=16.438$, $p<0.001$), demonstrating that oral rinsing significantly improved comfort, with a very large effect size (Cohen's $d=3.32$).

The mean SPTDS score decreased to 1.31 ± 1.54 in the experimental group after oral rinsing, compared to 8.59 ± 2.15 in the control group's second measurement. The difference was statistically significant ($t=-19.269$, $p<0.001$), indicating that oral rinsing significantly reduced thirst-related discomfort, with a very large effect size (Cohen's $d=3.89$).

The mean number of bowel sounds increased to 5.98 ± 1.61 in the experimental group after oral rinsing, whereas it was 3.86 ± 1.22 in the control group's second measurement. This difference was statistically significant ($t=7.334$, $p<0.001$), suggesting that oral rinsing enhanced bowel motility, with a large effect size (Cohen's $d=1.48$).

Within-group comparisons showed that in the experimental group, post-rinsing measurements demonstrated an increase in comfort level, a decrease in thirst-related discomfort, and an increase in bowel motility compared to pre-rinsing values. In contrast, no significant changes were observed between the two measurements in the control group.

These findings indicate that oral rinsing led to significant improvements in comfort, reduction of thirst-related discomfort, and stimulation of bowel motility in the experimental group, while no meaningful changes occurred in the control group.

CONCLUSION

In conclusion, oral rinsing with plain water is an effective, cost-free, and easily applicable method for reducing postoperative thirst discomfort, enhancing comfort, and accelerating bowel movements. It is recommended that this practice be integrated into routine care in surgical clinics.

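### The stated inputs (effect size 0.50, alpha 0.05, power 0.85) do not give 41 per group for the independent t-test: if 0.50 is Cohen's d, 73 (two-sided) or 59 (one-sided) are needed

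*Combined protocol and SAP*

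**What the plan says.** In Study Population and Sample, the basis of the calculation is given as "The sample size was calculated using G*Power 3.1.9.7 software by a biostatistics expert". The inputs are introduced by "With an effect size of 0.50", followed by alpha 0.05 and power 0.85 (beta 0.15), with 1:1 allocation. The result is that "the required sample size was determined to be 82 patients (41 in the intervention group and 41 in the control group"). The margin above that figure is explained separately: "The actual study was completed with 98 patients (49 per group), considering potential data loss". The section does not state the test, one or two tails, the metric of the effect size, any correlation between measurements, or the outcome.

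The Data Analysis section gives the between-group method: "A t-test for independent samples was used to determine the mean differences between two independent groups". It also says that "a single-factor analysis of variance (ANOVA) was used for repeated measures". Cohen's d appears there as the metric for the observed effects: this "effect size was calculated to assess the significance of the difference between the groups in terms of the intervention". The RESULTS section reports the post-rinse group differences as t statistics with Cohen's d.

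**The concern.** A reader who enters 0.50, 0.05 and 0.85 for a two-group t-test does not get 41 per group. The gap is 18 patients per group one-sided (59 − 41) and 32 two-sided (73 − 41), so it is not rounding. The allowance for data loss cannot explain it either: such an allowance raises a required number, and here it is applied after the 82 to reach 98.

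At stake is the stated type II error of 15%. For the between-group test that the document names, on the d = 0.50 reading, it would be about 39% at the planned size (two-sided). That is a design claim the reader should be able to reproduce. The reported results are not at stake.

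**Working it through.** **Inputs.** From Study Population and Sample: effect size 0.50, alpha 0.05, power 0.85, 1:1 allocation, 82 required, 98 completed. From Data Analysis: the independent-samples t-test. Assumed, because not stated: 0.50 is Cohen's d. Sidedness is not stated for the calculation, so both were run.

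**Attempt to reproduce the 82.** With n per group, the t-test has 2n − 2 degrees of freedom and noncentrality δ = d·√(n/2). Power is the noncentral-t probability beyond the critical value.

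A rough check uses the normal approximation, n = 2·[(z_α + z_β)/d]²:

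- Two-sided: 2·[(1.960 + 1.036)/0.5]² = 71.8, so 72.
- One-sided: 2·[(1.645 + 1.036)/0.5]² = 57.5, so 58.

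The exact solutions are 72.80 and 58.20, so 73 and 59 per group.

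| n per group | δ | Power, two-sided | Power, one-sided |
|---|---|---|---|
| 41 (planned) | 2.264 | 0.609 | 0.726 |
| 49 (completed) | 2.475 | 0.688 | 0.792 |
| 58 | 2.693 | – | 0.849 |
| 59 | 2.716 | – | 0.854 |
| 72 | 3.000 | 0.846 | – |
| 73 | 3.021 | 0.851 | – |

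The stated 82 is 82/146 = 56% of the two-sided requirement and 82/118 = 69% of the one-sided one. The two-sided type II error is 1 − 0.609 = 39.1% at 41 per group and 1 − 0.688 = 31.2% at 49. For 85% power at 41 per group, d would have to be about 0.67 two-sided or 0.60 one-sided.

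**Other procedures with the printed value of 0.50.** None of these gives 82:

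- Paired t-test: 38 pairs two-sided, 31 one-sided.
- One-way ANOVA with f = 0.50: 38 in total.
- Two-measurement repeated-measures ANOVA with f = 0.50: 8 to 33 in total for correlations of 0 to 0.7.
- Chi-square with w = 0.50 and 1 df: 36 in total.
- Correlation of 0.50: about 33.

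**Routes that do reach 82.** Each needs an input the document does not give.

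- *Between-factor repeated-measures ANOVA*, f = 0.25 (f = d/2 for two equal groups), λ = N·m·f²/(1 + (m − 1)ρ). With m = 2 and ρ = 0.10, N = 82 gives λ = 82·2·0.0625/1.10 = 9.32 and power 0.854. With equal groups the answer is 82 for ρ from 0.09 to 0.11, but 74 at ρ = 0 and 110 at ρ = 0.5. With m = 4 and ρ = 0.40, λ = 82·4·0.0625/2.20 = 9.32, so N = 82 again.
- *Baseline-adjusted comparison*, two-sided, d = 0.50: 41 per group at a pre–post correlation of about 0.67.
- *Change-score t-test*, one-sided, d = 0.50: 41 per group at a correlation of 0.65.

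**Bearing on the results.** Recomputing post-rinse d from the means and SDs in RESULTS, with the pooled SD for equal groups:

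- Comfort: (7.33 − 3.86)/√[(1.14² + 0.94²)/2] = 3.32.
- Thirst discomfort: (8.59 − 1.31)/√[(1.54² + 2.15²)/2] = 3.89.
- Bowel sounds: (5.98 − 3.86)/√[(1.61² + 1.22²)/2] = 1.48.

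All three match the reported values and are far above 0.50.

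**The case against.** The sample-size paragraph never says that 0.50 is Cohen's d or that the t-test was the basis. Both are inferred from the Data Analysis section, where d describes observed effects. The design is pre-test/post-test and a repeated-measures ANOVA is named, so another G*Power procedure may have been run. The Intervention Procedure section even says that in the pilot the instruments were given after every rinse. With a baseline that makes four measurements, and a four-measurement calculation at a correlation of 0.40 gives exactly 82. On this view only under-specification is certain, and with observed effects this large it is a small reporting matter.

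The first part stands to this extent: the shortfall is conditional on d = 0.50, and the document does not prove which procedure was run. The alternatives do not rescue the sentence as written. Each needs a correlation stated nowhere. The repeated-measures route also needs f = 0.25 where 0.50 is printed, and it tests the group difference averaged over all measurements, including the one before rinsing, which is not the post-rinse comparison that was reported. The pilot's repeated administration is described only for the experimental group, and the main study measured twice; with two measurements at the same correlation of 0.40 the requirement is 104, more than the 98 completed. Baseline-adjusted and change-score analyses are not named in the Data Analysis section.

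The point about practical weight also stands: no post-rinse null result needs explaining, and no reported between-group conclusion changes.

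**Conclusion.** The concern holds. Taking 0.50 as Cohen's d, alpha 0.05 and the independent-samples t-test, 85% power needs 73 per group two-sided or 59 one-sided. Neither the 82 planned nor the 98 completed delivers the stated power under either sidedness. If 0.50 was not d for this test, the 82 rests on undisclosed inputs and on an analysis other than the reported post-rinse t-tests. In both cases the sentence needs correcting. The matter is confined to a stated design figure.

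**What to change.** Check the G*Power output, then restate the sentence in one of two ways.

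1. If the independent t-test with d = 0.50 was the basis, for example: *For [named outcome], a two-sided independent-samples t-test with d = 0.50 and alpha = 0.05 has about 61% power with 41 per group and 69% with the 49 per group completed; the previously stated 85% was incorrect.*
2. If another procedure was used, report from its output the test, tails, effect-size metric and value, number of measurements, assumed correlation and outcome, and align that procedure with the Data Analysis section.

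The effect detectable with 85% power two-sided (d = 0.67 at 41 per group, 0.61 at 49) may be added if it is labelled a post-hoc sensitivity figure and not presented as the planning effect size.

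The cost is one sentence, plus retrieval of the G*Power output. Under option 1 the stated power becomes less favourable. Enrolment, analysis and reported results are unchanged.

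### The time of the first assessment after surgery is neither fixed nor described as recorded, so comparable timing between the arms cannot be verified; this matters mainly for bowel sounds

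*Combined protocol and SAP*

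**What the plan says.** Intervention Procedure gives the starting point for each arm. For the rinsing arm: "In the experimental group, postoperative cognitive assessment was conducted". For controls: "In the control group, postoperative cognitive assessment was also conducted". The first forms and auscultation follow in both arms. The interval to the second reading is described (15 minutes after the last of three rinses; 75 minutes in controls), but no hour, window or event after surgery fixes when the first reading takes place. Nothing there says whether the readings come before or after the patient first drinks.

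Data Collection Tools, item 2, describes the form: "The first section consisted of seven questions covering the patient's descriptive characteristics, including age, gender, and education level". The clinical items are "diagnosis, preoperative fasting time, postoperative oral intake time, and the time to start oral intake". The other part of the form is a chart: "The second section included a chart created for recording bowel sounds". Its fields are not described.

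Data Analysis lists independent and paired t-tests and a repeated-measures ANOVA. It names no covariate for time since surgery. Results then reports of bowel sounds before any rinse that "the difference in bowel sound frequency was significant", with controls higher.

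**The concern.** Thirst, comfort and bowel sounds can all be expected to change in the hours after an operation. If one arm tended to be assessed earlier in recovery than the other, the comparison would mix stage of recovery with rinsing. Randomisation balances the patients. It does not balance a start time that is settled after allocation and that no rule governs.

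At stake is the statement in Results that rinsing enhanced bowel motility, and the claim in Conclusion that it accelerates bowel movements and belongs in routine care. Those statements rest on one-minute counts taken at unstated times from arms that were unequal at the outset. If the times were not kept, the comparison can be neither checked nor adjusted for timing.

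**Working it through.** **What the form holds.** Age, gender and education make 3 items; diagnosis, preoperative fasting time, postoperative oral intake time and time to start oral intake make 4; 3 + 4 = 7, the stated number of questions. None is time from end of surgery to assessment.

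**Baseline bowel sounds (Results, n = 49 per arm).** Means ± SD are 3.49 ± 1.06 and 4.06 ± 1.52.
- SE = √[(1.06² + 1.52²)/49] = √(3.434/49) = 0.265.
- t = 0.57/0.265 = 2.15 on 96 df, p about 0.034.
- d = 0.57/√(3.434/2) = 0.57/1.310 = 0.435. The document prints 0.44 and p < 0.05, so its figure reproduces.
- Three baseline outcomes were tested. If they were independent (an assumption), the chance that at least one gives p ≤ 0.034 is 1 − 0.966³ = 0.10.

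**Second reading.** 5.98 ± 1.61 and 3.86 ± 1.22: t = 2.12/√[(1.61² + 1.22²)/49] = 2.12/0.289 = 7.35, d = 1.48 (printed 7.334 and 1.48).

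**Change in bowel sounds.** Rinsing arm 5.98 − 3.49 = +2.49; control arm 3.86 − 4.06 = −0.20; difference in change 2.69.

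The documents give no pre-post correlation r, so it is varied. The variance of change in each arm is s₀² + s₁² − 2r·s₀·s₁. The SE of the difference in change is the square root of the sum of the two variances divided by 49. The baseline-adjusted estimate is 2.12 + 0.57b, with b = r(1.06 × 1.61 + 1.52 × 1.22)/(1.06² + 1.52²) = 1.037r.

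| r (assumed) | SE | 95% CI for 2.69 | Baseline-adjusted estimate | Upper 95% limit, control change |
|---|---|---|---|---|
| 0 | 0.392 | 1.91 to 3.47 | 2.12 | +0.36 |
| 0.5 | 0.284 | 2.13 to 3.25 | 2.42 | +0.20 |
| 0.9 | 0.150 | 2.39 to 2.99 | 2.65 | 0.00 |

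Drift at the rate seen in the controls therefore does not account for +2.49.

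**Thirst and comfort.** The SPTDS changes by 1.31 − 8.00 = −6.69 against 8.59 − 8.14 = +0.45. VAS comfort changes by 7.33 − 3.59 = +3.74 against 3.86 − 4.02 = −0.16. The baselines were similar (printed p = 0.801 and 0.165).

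**Oral intake times.** Results says that "in the control group it ranged between 2–66 hours". The same section then puts 88% of controls in 6–24 h, 8% in 24–48 h and 4% beyond 48 h. These sum to 100% and leave no control before 6 h. Counts of 43, 4 and 2 against 49, 0 and 0 have expected values of 46, 2 and 1 per arm and give χ² = 2(9/46) + 2(4/2) + 2(1/1) = 6.391, the printed value. The 2 h minimum and the categories cannot both be right as labelled.

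**The case against.** The strongest reply is the design. Patients were randomised 1:1 within diagnosis strata, and controls had their own second reading after 75 minutes. That removes ordinary recovery in expectation, and the control arm stayed flat. A reader might infer that recovery cannot be separated from rinsing at all; the documents do not support that. What remains is differential timing, and nothing shows that it occurred. The reply does not close the gap, however: a flat control course shows little drift at the stage when controls were assessed, not what unrinsed patients would do at the other arm's stage if the stages differed.

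Four further inferences are tempting and should not be drawn.

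- That the printed data reveal a timing imbalance. Higher control bowel sounds at baseline would suggest that controls were further into recovery, while their later oral intake (mean 15.20 v 10.41 h) would suggest slower recovery. The two do not point to one imbalance. Intake was observed after allocation, may itself respond to rinsing, and does not date the assessments. The baseline gap also runs against the rinsing arm: 2.12 at the second reading against 2.69 in change.
- That a control drinking at 2 h was first assessed within 120 − 75 = 45 minutes of surgery, or was re-tested after drinking. This assumes that intake time runs from end of surgery, and it uses a minimum that the category table contradicts.
- That researchers who knew the allocation chose when to start. The document says only that researchers collected data face-to-face; it does not say who set the start.
- That the times certainly were not recorded. Two of the seven items look alike, so the list may not be a firm inventory, and the bowel-sound chart might hold clock times. The supportable statement is that the form is not described as recording them.

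**Conclusion.** The concern holds in a limited form. Comparable timing after surgery is neither ensured by the procedure nor verifiable from the tools described, and the order of the readings relative to first oral intake is open. Differential timing therefore remains a possible confounder, chiefly for bowel sounds.

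The bowel-sound difference in change is 2.69, with a 95% CI no wider than 1.91 to 3.47 for assumed correlations from 0 to 0.9. The part due to timing, if any, cannot be calculated without the times. The baseline difference (p about 0.034) is compatible with different stages of recovery and equally with chance. The thirst and comfort differences are too large, and their baselines too similar, for timing to be a likely explanation.

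These figures rest on the printed means and SDs with 49 patients per arm.

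**What to change.** **For reuse of the plan.** Set one common measurement window after surgery for the first assessment in both arms. Add to the form the clock times of end of surgery, both readings and first oral intake. Schedule both readings before the patient's first intake, without changing when patients drink.

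**For the completed trial.** Establish whether end-of-surgery and assessment times can be recovered; the documents name no source for them. If they can, tabulate hours since surgery by arm, repeat the bowel-sound comparison with baseline bowel sounds and hours since surgery as covariates, and flag any second reading taken after intake. If they cannot, report the baseline-adjusted comparison and state unverified timing as a limitation on the bowel-motility conclusion. In either case, reconcile the 2 h control minimum with the intake categories in Results.

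**Cost.** A few added form fields for reuse. For the completed trial, a search for times in 98 patients and one further model. The bowel-motility claim may become weaker.

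### The pre-test is described inside already named arms with no concealment or blinding, so within-arm gains in bowel sounds rest on an unprotected baseline (3.49 v 4.06); the reported post-test comparison is not enlarged by this gap

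*Combined protocol and SAP*

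**What the plan says.** Study Design calls this a "randomized controlled trial with pre-test and post-test design, involving intervention and control groups". On allocation, Study Population and Sample says: "Eligible patients were stratified based on diagnosis and randomized using block randomization with a random number table in a 1:1 allocation ratio". It does not say when a patient's allocation was revealed relative to the pre-test.

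Intervention Procedure then describes the arms in turn. In the paragraph on the experimental group, the cognitive screen comes first and then the rinsing instruction, and "Data collection forms were administered face-to-face before the first rinse and 15 minutes after the final rinse, and bowel sounds were auscultated". In the paragraph on the control group, "patients scoring 23 or higher on the MMSE were administered the data collection forms and had their bowel sounds auscultated", with a repeat 75 minutes later. The section says that the researchers collected the data in person. It does not say who supervised the rinsing, or whether the person listening for bowel sounds knew the arm.

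The bowel-sound count is standardised by stethoscope model and a one-minute listening time. Data Analysis names independent t-tests, paired t-tests and a single-factor repeated-measures ANOVA, but no baseline-adjusted comparison of the arms. RESULTS reports similar baseline comfort and thirst scores, and then: "However, the difference in bowel sound frequency was significant ($p<0.05$), favoring the control group". It later reports the rise in bowel sounds within the rinse arm as a finding alongside the post-test comparison.

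**The concern.** A baseline is useful in a randomised trial because allocation cannot have influenced it. That is guaranteed when it is recorded before the allocation is opened. Otherwise it depends on the assessor and the patient not knowing the arm. Here the first readings are described within arms that already have names, and neither safeguard is mentioned. A one-minute listened count depends on the assessor, and the two interview scores depend on what the patient expects.

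The one baseline measure that differs significantly is the listened count, and it is lower in the arm about to rinse. A low start makes that arm's rise look larger. If the gap is chance, adjusting for baseline is right and the raw post-test difference is, if anything, slightly too small. If knowledge of the arm produced the gap, change scores and baseline adjustment carry that bias into the estimate. The document does not give the information needed to tell these cases apart.

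**Working it through.** **Inputs.** All means and SDs are from RESULTS; 49 per arm is from Study Population and Sample. Bowel sounds, rinse arm: 3.49 (SD 1.06), then 5.98 (SD 1.61). Control arm: 4.06 (SD 1.52), then 3.86 (SD 1.22). The pre-post correlation r is not reported; it is assumed to lie between 0 and 0.9.

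**1. Reproducing the reported baseline gap.**
- Difference = 3.49 - 4.06 = -0.57.
- SE = √((1.06² + 1.52²)/49) = √(3.434/49) = 0.265.
- t = -0.57/0.265 = -2.15 on 96 df, p = 0.034; 95% CI about -1.10 to -0.04.
- d = 0.57/√(3.434/2) = 0.435. Rounding of the inputs allows 0.426 to 0.444.

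The stated p<0.05 and d = 0.44 reproduce. The other two baseline tests also reproduce within rounding: comfort |t| = 1.405 (stated 1.399), thirst t = -0.248 (stated -0.253).

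**2. Reproducing the reported post-test result.**
- Difference = 5.98 - 3.86 = 2.12.
- SE = √((1.61² + 1.22²)/49) = 0.289; t = 7.35 (stated 7.334); d = 1.48, as stated.
- 95% CI = 2.12 ± 1.985 × 0.289, about 1.55 to 2.69.

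The first readings do not enter this calculation.

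**3. Where the baseline gap enters.**
- Rinse-arm gain = 5.98 - 3.49 = 2.49; control change = 3.86 - 4.06 = -0.20.
- Difference in change = 2.49 - (-0.20) = 2.69.
- Excess over post-only = 2.69 - 2.12 = 0.57, exactly the baseline gap; 2.69/2.12 = 1.27, or 27% more.
- Measured from the pooled baseline, (3.49 + 4.06)/2 = 3.775, the rinse-arm gain would be 5.98 - 3.775 = 2.21, not 2.49.

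**4. Baseline-adjusted estimate from summary data.** Adjusted difference = 2.12 - b × (-0.57), where b = r × (1.06 × 1.61 + 1.52 × 1.22)/(1.06² + 1.52²) = r × 3.561/3.434 = 1.037r.

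| Assumed r | b | Adjusted difference |
|---|---|---|
| 0 | 0 | 2.12 |
| 0.3 | 0.311 | 2.30 |
| 0.5 | 0.518 | 2.42 |
| 0.7 | 0.726 | 2.53 |
| 0.9 | 0.933 | 2.65 |

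The t values over this range run from 7.1 to 17.3.

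**5. Could the gap be chance?** With three independent baseline tests at 0.05, the probability of at least one significant result is 1 - 0.95³ = 0.143. Independence is an assumption.

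**The case against.** Describing a completed two-arm trial one arm at a time is ordinary reporting style and need not give the order of events. Randomisation timing is not stated, so a baseline after allocation is an inference. **This stands.**

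A reader might also infer that the people who ran the rinsing took the baseline and knew what would follow. The text supports only that the researchers collected the data. Who gave the instruction to rinse, and what the assessor knew, are not recorded. **This stands too**, so the authors should not be asked to declare that the arm was known.

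The evidence for an artefact is weak. Expectation should make the rinse arm look thirstier at the start, yet its thirst score is slightly lower (8.00 v 8.14, p = 0.801). Comfort leans the predicted way (3.59 v 4.02) but is not significant (p = 0.165).

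The 2.69 appears nowhere in the document. The reported bowel-sound effect already uses second readings, and the within-arm change is described in words without a size. The shift of 0.57 is about the half-width of the 95% interval around 2.12, and no handling of the baseline reverses the result. **All of this stands.**

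It does not remove the point. Paired tests are a named analysis, and RESULTS uses the within-arm rise to support its reading that rinsing stimulates the bowel. Those results take the first count at face value. The imbalance is reported but not carried into that interpretation.

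**Conclusion.** The point holds in a limited form. As written, the baseline is not shown to be protected from knowledge of the arm, and one of its three readings differs by 0.57 sounds (p = 0.034). Chance is a sufficient explanation; bias is possible and cannot be excluded from what is documented.

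The consequence is confined to the within-arm gain and to any change-based contrast, which would be 2.69 instead of 2.12. A tempting stronger reading is that the imbalance inflates the trial's bowel-sound effect. The document does not support that: t = 7.334 and d = 1.48 compare second readings only. With a positive pre-post correlation, the lower start works against the rinse arm in that comparison, and adjustment raises the estimate. The baseline gap therefore cannot explain the between-group difference. The absence of any described blinding at the second reading is the larger threat to that result, and it is a separate matter.

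The adjusted range of 2.12 to about 2.65 rests on the assumed correlation of 0 to 0.9 and on a baseline unaffected by allocation.

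**What to change.** **Procedure, for any further use.** Complete both forms and the first auscultation before that patient's allocation is opened; then allocate; then rinse or wait. Staff, forms and visits stay the same. The cost is that allocation has to be opened at the bedside after the pre-test. This cannot be applied to data already collected.

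**Data in hand.**
- State when allocation was revealed relative to the pre-test, who took the baseline readings, and whether they knew the arm.
- Rest the bowel-sound conclusion on the between-group comparison and not on within-arm gains.
- Report a baseline-adjusted (ANCOVA) difference from the patient-level data beside the post-only 2.12. Say that adjustment corrects a chance imbalance but is valid only if allocation did not affect the baseline.

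The cost is a few sentences of clarification and one further line of results.
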